**Please save frequently**

- c) Describe the study design (e.g., single/double blind, parallel, crossover, control, experimental, observational, etc.). If the study is investigator-initiated, a timeline for individual subject recruitment, follow-up, and analysis for the study is required. Also, indicate if the subjects will be randomized.

Our study is a prospective comparison between absorbable hemostatic agents as a group and the body's natural hemostatic ability without aid of therapy in patients undergoing bilateral sinus surgery with or without septoplasty.

We calculated the sample size and power analysis in the following way:

Given the number of statistical tests, we calculated a Bonferonni correction to set the alpha for the analysis at 0.017 (alpha originally at .05 divided by the number of tests = .05/30 = 0.017). Using G-Power statistical software, power analyses were completed using the Means: Wilcoxon-Mann-Whitney test (two groups). Given alpha at 0.017 and Power at 0.80, we determined that a total of 244 participants (122 in the control group, 122 in the hemostatics group) would be needed to detect a medium effect size (d=0.5). Since one nostril will be used as the control and the therapy applied to the other side, the number of participants needed drops to 122.

Based on previous studies, we conservatively expect a dropout rate of 15%. In order to maintain the same number of participants, we would need to enroll a total of 144 participants

Postoperatively, patients will rate subjective symptoms such as nasal obstruction, bleeding,

**Protocol Title:** Analysis of hemostatic agents compared to physiologic hemostasis

---

pain, and nasal discharge on a scale ranging from 1-10, of which 10 is the most severe. Similarly, the treating physicians on endoscopic examinations will rate objective measures such as mucosal edema, infection, time spent debriding, and synechiae formation. (Please see the attached patient and physician questionnaires) Patient questionnaires will be completed on postoperative days #1, 2, 7, and 14. Surgical healing outcomes will be noted during routine postoperative visits 1 and 2 weeks after surgery. Expected total duration of each subjects' participation is 6 weeks. Total subject accrual should take no longer than one year. Data analysis will take up to three months. Estimated time of completion is 03/2018.

d) **If subjects will be given placebo, please justify placebo use. \*?HELP?\***

N/A

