**If No, explain what SLU will NOT participate in:**

**Please save frequently**

Page numbers from a sponsor's protocol/grant may be referenced in 3b, 3c, and 3d.

- b) **Describe all the procedures, from screening through end-of-study, that the human subject must undergo in the research project, including study visits, drug treatments, randomization and the procedures that are part of standard of care. Specify which procedures are for research and which are standard of care. Please note: The box below is for text only. If you would like to add tables, charts, etc., attach those files in the Attachment section (#16).**

a.) Patients will have (standard of care) Endoscopic Sinus Surgery.  
 b.) Each patient will receive a hemostatic agent in one nostril and nothing in the other nostril.  
 c.) Products will be placed in patients' post-operative sinus cavities at the end of the procedure according to company recommended instructions. Essentially all products placed in the middle meatus are allowed to remain there until absorbed or removed at a post operative visit on weeks 1, 2, and 6. Post-operative irrigations (Standard of Care) will remove much of the material. Any residual material is removed in the office on normal, (Standard of Care) post-operative debridement on weeks 1, 2, and/or 6.  
 d.) Subjects will provide subjective pre- and post-operative data, such as rating their pain, bleeding, obstruction, and discharge on days 0, 1, 2, 7, and 14 (Standard of Care).  
 e.) Patients will be given a questionnaire packet pre-operatively (Research Related). Questionnaires will include post-operative data on days 0, 1, 2, 7, and 14. They are asked to bring completed questionnaires on standard post-operative visits.  
 f.) The physician will record objective and subjective data (synechiae, edema, infection, granulations, and time spent debriding) upon regular reexamination of the sinuses after surgery, at post-operative visits on weeks 1, 3, and 6. All procedures are standard clinical care.  
 g.) Follow up visits will conform to standard clinical care; patients will be seen in the physician's clinic.

**Protocol Title:** Analysis of hemostatic agents compared to physiologic hemostasis

---

clinic.

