- c) If the proposed study is a clinical trial where a drug, vaccine, device or other treatment is compared to a placebo group or comparison treatment group, what are the guidelines or endpoints by which early decisions regarding efficacy or lack of efficacy can be made? For example, it may be reasonable to stop enrollment on a study when efficacy has already been clearly demonstrated, to avoid unnecessary enrollments of additional subjects. Alternatively, it may be reasonable to stop enrollment when it is clear that efficacy will never be demonstrated, given the statistical power of the study as designed. Describe the guidelines that are in place to assist in making these determinations, if relevant to the proposed study.

If side effects or discomforts do occur, [name] and/or [name] will try to minimize and treat these by irrigating the treated sinus with saline to remove the Arista, Nexfoam, Sinufoam, Nasopore, Posiseq, or Posiseq X.

- d) Describe how data analysis will be performed (statistical tests, methods of evaluating data) and indicate the smallest group/unit for which separate reporting will occur. For studies involving a questionnaire, if data and reliability information are available, please describe or provide references. For full board, unfunded studies describe sample size determination and power analysis. If none, please justify.

Means and standard deviations will be obtained for data collected from patients and the physician. These outcomes will be used for comparative evaluation of hemostatic agents (n=144) against no therapy. Statistics will include descriptive statistics and a non-parametric ANOVA comparing the questionnaire patient data and the physician data followed by Post-hoc multiple comparisons.

Please save frequently

- e) State if deception (including incomplete disclosure of study purpose/procedures) will be used. If so, describe the nature of the deception and provide a rationale for its use. Also, describe debriefing procedures or justify a waiver of the requirement to debrief. NOTE: for studies using deception, an alteration of consent must be justified in the Informed Consent section of the protocol (#13) and the debriefing script/statement must be uploaded in the Attachments section (#16). See IRB Deception Guidelines.

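### The Bonferroni divisor of 30 is not itemised and does not agree with the plan's own outcome schedules, which conflict between sections 2c and 3b

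*Combined protocol and SAP*

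**What the plan says.** Section 2c (study design and sample size) derives the threshold as "alpha originally at .05 divided by the number of tests = .05/30 = 0.017" and carries it into the power calculation: "Given alpha at 0.017 and Power at 0.80". The calculation is for a two-group Wilcoxon-Mann-Whitney test with d = 0.5. It gives 122 per group, read as 122 patients because each patient supplies both nostrils, and 144 after 15% dropout. The 30 tests are not listed.

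Two places describe what is measured and when:

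- **Section 2c.** Four patient symptoms are named, on postoperative days 1, 2, 7 and 14. Four physician measures are named (edema, infection, debriding time, synechiae), at 1 and 2 weeks. Both lists are introduced as examples, and the reader is sent to attached questionnaires.
- **Section 3b.** Item d has patients giving pre- and post-operative data, "such as rating their pain, bleeding, obstruction, and discharge on days 0, 1, 2, 7, and 14". Item e describes the questionnaires as holding post-operative data on those same five days. Item f has the physician record five measures, granulations being the addition, "upon regular reexamination of the sinuses after surgery, at post-operative visits on weeks 1, 3, and 6".

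Section 3d plans a non-parametric ANOVA "followed by Post-hoc multiple comparisons". It gives no number for these comparisons and does not say whether they belong to the 30.

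**The concern.** A Bonferroni threshold is only as good as the count behind it. Here the count is a bare number, and it matches neither schedule as written. If the divisor is smaller than the number of tests run, the family-wise error bound exceeds the intended 5%. If it is larger, power is given away. If no list exists, the family can be settled after the results are seen. The sample size also depends on the divisor, because 122 per group was computed at the resulting alpha.

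This point is about the divisor. The printed quotient is a separate slip: 0.05/30 is 0.00167, and 0.017 is ten times too large. Correcting that decimal leaves the 30 unexplained.

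**Working it through.** **1. Reproduce the plan's figure.** Inputs from section 2c: 30 tests, power 0.80, d = 0.5, two equal groups, rank test. Sidedness is not stated. Method: noncentral t with the sample size scaled by the rank test's asymptotic relative efficiency for normal data, 3/π.

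- Effective n per group: 122 × 3/π = 116.5
- Degrees of freedom: 2 × 116.5 − 2 = 231
- Noncentrality: 0.5 × √(116.5/2) = 3.816
- Alpha: 0.05/30 = 0.00167. The one-sided critical t is 2.966 and power is 0.801.

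The smallest n reaching 0.80 is exactly 122 one-sided, and 136 two-sided. At the printed 0.017 the requirement would be 75 one-sided or 89 two-sided. The sample size was therefore evidently computed at 0.05/30, one-sided. Dropout: 122/0.85 = 143.5, so 144, as stated.

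**2. Count the tests**, assuming one test per item per time point.

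- Section 2c, named items only: 4 × 4 + 4 × 2 = 24
- Section 3b, day 0 included: 4 × 5 + 5 × 3 = 35
- Section 3b, day 0 excluded as pre-operative: 4 × 4 + 5 × 3 = 31

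The physician list in 3b is closed, and its symptom list is open with four named. The 3b counts are therefore minima, and further symptoms would only move them further above 30. The 2c count is also a minimum, so 30 is reachable there if the questionnaires add items. One mixture gives exactly 30: the 3b items and days with the two visits of 2c, 4 × 5 + 5 × 2. No section states that schedule.

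**3. Family-wise bound if every test uses 0.05/30** (number of tests × alpha).

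- 24 tests: 24 × 0.05/30 = 0.040
- 31 tests: 31 × 0.05/30 = 0.052
- 35 tests: 35 × 0.05/30 = 0.058

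**4. Alpha, n and power if the divisor follows the count.** The method is that of step 1. Entries are one-sided / two-sided.

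| Tests | Alpha = 0.05/tests | n per group for 0.80 power | Power at 122 per group |
|---|---|---|---|
| 24 | 0.00208 | 118 / 132 | 0.820 / 0.758 |
| 30 | 0.00167 | 122 / 136 | 0.801 / 0.736 |
| 31 | 0.00161 | 123 / 137 | 0.798 / 0.733 |
| 35 | 0.00143 | 125 / 139 | 0.787 / 0.721 |

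With 15% dropout, one-sided: 123/0.85 = 144.7, so 145; and 125/0.85 = 147.1, so 148. Both are slightly above the 144 fixed in section 8b.

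**The case against.** The strongest reply is that no error has been demonstrated. The lists in 2c and the symptom list in 3b are illustrative, the questionnaires are not in the text, and the plan nowhere says that each item is tested at each time point. Time might be a factor within the ANOVA of 3d, which would change the count. This stands in part. A reader might infer that 30 is simply wrong, and the documents do not support that. They do show that 30 does not fit 3b at one test per item per time point, because open wording can only raise that count, and that the two sections contradict each other.

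Three other inferences go too far:

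- **Day 0 is baseline, so testing it wastes alpha.** Item d of 3b points that way, but item e calls the day 0 data post-operative, and day 0 could be the evening of surgery. Both readings have to be carried.
- **The 30 leaves out the post-hoc comparisons, and control of error is lost.** Since the 30 is not itemised, nobody can say what it includes. The number of post-hoc comparisons is not given, any multiplication by pairs of agents would be an assumption, and such tests are often run after a significant overall test with their own adjustment. The plan's stated comparison is agents as a group against nothing.
- **The 122 is invalid because of the count.** Step 4 shows it moving by at most 4 per group one-sided. Undeclared sidedness moves it more (136 against 122 at 0.05/30).

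Against the 24 named items of 2c, dividing by 30 is in fact conservative.

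**Conclusion.** The point holds as a mismatch to be reconciled. The divisor is unsupported: it is not itemised, it equals neither section's own count, and the sections conflict on day 0, physician visits and granulations. The numerical consequence is small. Under the 3b schedule the family-wise bound is 0.052 to 0.058 in place of 0.05. At an alpha matched to that schedule, power with 122 per group is 0.798 to 0.787 one-sided, or 0.733 to 0.721 two-sided. Most of the two-sided shortfall comes from sidedness, since at 30 tests two-sided power is already 0.736.

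These figures assume one test per item per time point, four symptoms in 3b, normal-parent efficiency for the rank test, and the plan's own two-group calculation. The questionnaires could supply a list of exactly 30. It is still worth correcting, because the threshold for every claim in the trial depends on a count that the reader cannot check.

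**What to change.** In sections 2c, 3b and 3d:

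1. Reconcile the items and visits, so that granulations, day 0 and the physician visit weeks read the same throughout, and say whether day 0 is before or after surgery.
2. Add a short table of the confirmatory outcome-by-time tests and set the divisor to its row count.
3. Restate alpha from that count (0.05/35 = 0.0014 to 0.05/24 = 0.0021 on the present schedules, not 0.017). Declare one- or two-sided testing and give the resulting power at the available sample size.
4. State whether the post-hoc comparisons in 3d are inside that family, and so counted, or descriptive.

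The cost is one table and a few restated figures, with no new data. The continuing-review entry under Expedited Paragraphs marks the remaining activity as data analysis only. If that is the current status, the sample size is fixed and the useful step is to settle the family and threshold before the comparisons are run.

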**1. Background**

**Protocol Title:** Analysis of hemostatic agents compared to physiologic hemostasis

---

Page numbers from a sponsor's protocol/grant may be referenced in 1a and 1b.

- a) **Provide an introduction and background information. Describe past experimental and/or clinical findings leading to the formulation of the study, if applicable. Investigator Initiated studies must cite references in the response provided or attach a bibliography. *\*?HELP?\****

In this study we wish to determine if the use of hemostatic agents after endoscopic sinus surgery is superior to no agent at all. We will treat patients with one of many different FDA approved hemostatic agents in one of their nostrils and compare it to a side in which no therapy is applied. We will then evaluate qualities of the patient's recovery (synechia formation, granulation, edema, infection, and time spent debriding the sinuses) in response to intervention.

Functional endoscopic sinus surgery (ESS) is a safe, commonly performed procedure primarily in an outpatient setting. One of the most prevalent complications is post-operative epistaxis. To prevent this nasal packing is often employed. Traditionally non-absorbable packing was employed; yet, this has fallen out of favor with most otolaryngologists considering the great discomfort of the packing, especially upon removal (von Schoenberg). In addition to this, with removal of non-absorbable packing interruption of the wound bed is inevitable. This has led to a paradigm shift towards absorbable packing, which are biomaterials that provide substrate to stimulate clotting. Absorbable hemostatic agents tend to spare the mucosa and are less painful upon removal (Maccabee). However, absorbable packing comes with the possible drawback of increased rates of synechia formation secondary to initiation of local inflammation (Valentine). Standard of care is no packing, one of these types of absorbable packing, or removing packing.

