**Unknown Side Effects**

There is always the risk of developing previously unknown side effects.

Patients may encounter these risks regardless of participation in this research study.

If side effects or discomforts do occur, [name] will try to minimize and treat these by irrigating the

**Protocol Title:** Analysis of hemostatic agents compared to physiologic hemostasis

---

treated sinus with saline to remove the Arista, Nexfoam, Sinufoam, Nasopore, Nexfoam, Posisep and Posisep X.

The investigator is willing to discuss any questions the participant might have about these risks and discomforts.

6. Describe any risks related to the use of radioisotopes/radiation-producing machines (e.g., X-rays, CT scans, fluoroscopy).

7. Describe why this investigational compound/drug/device/procedure's risks/benefits are potentially better than standard of care or other common alternatives. Any standard treatment that is being withheld must be disclosed and the information must be included in the consent form. **\*?HELP?\***

There is conflicting data in previous studies whether hemostatic agents are better than treatment with nothing or all. The goal is to answer that question definitively. Other options are to have both sides treated with a hemostatic, have neither side treated, or to place non-absorbable packing material that requires later removal.

8. Describe any psychological, social, or legal risks the subject may experience. **\*?HELP?\***

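### The 122 per group matches a one-sided calculation at alpha 0.00167, but sidedness is never stated and the planned analysis is non-directional; the same unpaired calculation done two-sided gives about 74% power, not 80%.

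*Combined protocol and SAP*

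**What the plan says.** Section 2c sets the significance level by a Bonferroni division, in these words: "set the alpha for the analysis at 0.017 (alpha originally at .05 divided by the number of tests = .05/30 = 0.017". The calculation was done in G-Power for a two-group Wilcoxon-Mann-Whitney test with a medium effect of d=0.5: "Given alpha at 0.017 and Power at 0.80, we determined that a total of 244 participants" would be required, split as "122 in the control group, 122 in the hemostatics group". Because each patient supplies a treated and an untreated side, the protocol halves 244 to 122 patients, then raises this to 144 for 15% dropout. Neither the sidedness of the test nor the parent distribution is given.

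Section 3d plans "a non-parametric ANOVA comparing the questionnaire patient data and the physician data followed by Post-hoc multiple comparisons". It gives no sidedness either.

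On direction, section 1a frames the question as whether an agent is superior to none, but also warns that "absorbable packing comes with the possible drawback of increased rates of synechia formation secondary to initiation of local inflammation". Section 9, item 7 adds: "There is conflicting data in previous studies whether hemostatic agents are better than treatment with nothing or all".

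**The concern.** A power figure is informative only for the test that will be used. If 122 came from a one-sided calculation, the stated 80% does not carry over to a non-directional analysis at the same alpha.

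Direction also matters clinically here. The physician-rated outcomes include synechiae, edema, granulation and infection, and the background gives a reason why packing might worsen the first of these. A test that looks only for benefit could not declare such a harm. With sidedness unstated in both 2c and 3d, the threshold is also open. At 0.00167 the critical z is 2.94 one-sided and 3.14 two-sided, so a result favouring the agents that falls between those values would be significant on one reading and not on the other.

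**Working it through.** **Inputs from section 2c:** two-group Wilcoxon-Mann-Whitney test, d = 0.5, power 0.80, 122 per group, alpha printed as 0.017 and derived as .05/30. The division gives .05/30 = 0.00167; 0.017 is about .05/3. **Not stated:** sidedness and parent distribution.

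**Method.** Asymptotic relative efficiency (A.R.E.) approach: replace n per group by n′ = n × A.R.E. (3/π = 0.955 for a normal parent), then use a noncentral t with 2n′ − 2 degrees of freedom and noncentrality d·√(n′/2).

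**Step 1: reproduce 122.** With n = 122, n′ = 116.5, df = 231 and noncentrality 0.5 × √(116.5/2) = 3.816.

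| Alpha | Sides | n per group for 80% power | Power at 122 per group |
|---|---|---|---|
| 0.017 (printed) | one | 75 | 95.3% |
| 0.017 (printed) | two | 89 | 92.0% |
| 0.00167 (.05/30) | one | **122** | 80.1% |
| 0.00167 (.05/30) | two | 136 | 73.6% |

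At 0.00167 the critical t is 2.966 one-sided and 3.181 two-sided. One-sided, 121 per group gives 79.7% and 122 gives 80.1%, so 122 is the exact minimum. Rounding alpha to 0.0017 also gives 122 one-sided and 136 two-sided.

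**Step 2: could another setting give 122?** Two-sided at 0.00167, by parent or efficiency assumption:

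- plain t-test: 130
- minimum efficiency (0.864): 150
- Laplace: 87
- logistic: 119 (81.8% power at 122)

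The logistic result is near but different. Among the settings tried, only one-sided with a normal parent at .05/30 (or 0.0017) returns 122.

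**Step 3: two-sided cost within the protocol's own unpaired calculation.** Power falls from 80.1% to 73.6%. The effect detectable with 80% power at 122 per group rises from d = 0.50 to d = 0.53 (80.4% power at 0.53).

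**Step 4: the paired design.** For 122 pairs, the standardised mean difference is dz = 0.5/√(2(1 − ρ)), where ρ is the correlation between a patient's two sides. Signed-rank power uses n′ = 122 × 3/π = 116.5, df = 115.5 and noncentrality dz·√n′; the two-sided critical t at 0.00167 is 3.220. The protocol gives no ρ, so these values are assumptions:

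| ρ (assumed) | dz | Two-sided power |
|---|---|---|
| 0 | 0.354 | 72% |
| 0.1 | 0.373 | 79% |
| 0.2 | 0.395 | 85% |
| 0.3 | 0.423 | 91% |
| 0.5 | 0.500 | 98% |

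Power reaches 80% at ρ of about 0.12.

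**Step 5: enrolment.** 122/0.85 = 143.5, rounded up to 144. This agrees with the protocol.

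**The case against.** Several counter-arguments have force.

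- **One-sidedness is inferred.** No passage says the test was one-sided. The evidence is an exact match to unstated software settings, and a two-sided logistic parent comes close at 119. This stands as a limit on certainty, but 119 is not the printed figure and the one-sided normal setting is.
- **The question is worded directionally.** Section 1a asks about superiority, which lends a one-sided basis some support. That also stands. But the same section names a possible harm, and section 9, item 7 says earlier evidence conflicts, so a harmful result should be declarable.
- **At the printed alpha there is no shortfall.** At 0.017, two-sided power with 122 per group is 92%. True, but 0.017 is not the quotient the protocol writes and does not reproduce its sample size.
- **The practical cost may be nil.** Inclusion requires a similar degree of disease on both sides, which makes some positive correlation plausible, and a modest one restores 80%. The IRB checklist also marks the remaining work as data analysis only, so no enrolment decision depends on this. Both points limit the size of the problem. Neither supplies the missing sidedness or makes 80% the power of the planned test.

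Two stronger readings are tempting. One is that the trial's true power is 74%. That figure belongs to an unpaired test, whereas the design is within-patient, and the groups and time points in the planned ANOVA are not specified. The other is that the trial will be unable to declare harm, or that its family-wise error will rise. Both would require a one-sided analysis, or a direction chosen after seeing the data, and no passage plans either. Taken as written, the ANOVA in 3d has no direction and could detect an increase in synechiae.

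**Conclusion.** The point holds as a mismatch between a stated power and the planned test. The 122 per group is reproduced exactly by a one-sided, normal-parent calculation at alpha 0.00167, not at the printed 0.017. Done two-sided at 0.00167, the protocol's unpaired calculation has 73.6% power, about 6.5 percentage points less than the 80.1% one-sided, and would need 136 per group for d = 0.5.

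How far the trial itself falls short, if at all, cannot be settled from the documents. With 122 evaluable pairs, two-sided power is below 80% if the sides are nearly uncorrelated and well above it at a correlation of 0.2 or more. These results assume that .05/30 is the intended level, that the normal-parent efficiency of 3/π applies, and that d = 0.5 is measured against the per-side standard deviation. The unstated sidedness needs no such assumption: it is absent from both 2c and 3d.

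**What to change.** In sections 2c and 3d:

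1. Correct alpha from 0.017 to 0.00167 (.05/30).
2. State that every treated-versus-untreated test is two-sided at that level, so that benefit and harm, notably synechiae, can both be declared.
3. Replace the 80% claim with a two-sided paired calculation for 122 evaluable patients, showing power over a stated range of side-to-side correlation. Note beside it that the unpaired two-group calculation gives about 74% two-sided.
4. Keep 122 evaluable and 144 enrolled.

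The cost is a few sentences and one recalculation, with no added patients or data. The downsides are a slightly stricter threshold for claiming benefit (z of 3.14 rather than 2.94) and a stated power that may be slightly lower than 80% if the two sides are nearly uncorrelated.

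### The stated 80% power belongs to a two-independent-groups test that was then halved; the power of this within-patient design depends on a between-side correlation the plan never gives

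*Combined protocol and SAP*

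**What the plan says.** All of the sizing is in section 2c. The software and test are given in one sentence: "Using G-Power statistical software, power analyses were completed using the Means: Wilcoxon-Mann-Whitney test (two groups". The inputs are "Given alpha at 0.017 and Power at 0.80" and an effect described as "would be needed to detect a medium effect size (d=0.5". The result is "a total of 244 participants (122 in the control group, 122 in the hemostatics group". The plan then halves the total because one nostril serves as control for the other, so that "the number of participants needed drops to 122". A 15% dropout allowance raises this to 144 enrolled.

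Section 3b confirms that every patient has an agent on one side and nothing on the other. Section 8h requires disease of similar degree on both sides. Section 3d plans a non-parametric ANOVA with post-hoc comparisons and does not say whether it is paired. No section gives a within-patient correlation, a standard deviation of the side-to-side difference, a paired effect size or the sidedness of the test.

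**The concern.** Two sides of one nose are matched observations. They share the patient, the operation and the raters, and the eligibility rule selects for similar disease on both sides. The precision of the treated-minus-untreated comparison depends on the standard deviation of the within-patient difference, hence on rho. A two-group calculation contains no such term, and dividing its total by two does not supply one.

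What is at stake is interpretation. Someone reading a null result would take it that the trial had 80% power at d = 0.5. If the sides are positively correlated, the trial could detect a smaller effect than that statement implies. The unpaired framing could also carry over into the analysis, where it would forfeit the gain from pairing.

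**Working it through.** **Inputs from section 2c:** d = 0.5, power 0.80, 122 per group, dropout 15%. Alpha is printed as 0.017, but the division shown ("alpha originally at .05 divided by the number of tests = .05/30 = 0.017") equals 0.00167. **Assumed:** rho = 0, 0.3 and 0.5; normally distributed scores; d standardised by the between-patient SD.

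**Method.** The rank test is approximated by the t-test with n multiplied by its asymptotic relative efficiency, 3/π. For n = 122, m = 122 × 3/π = 116.5.

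**Step 1: reproduce the plan's figure (two groups).** Noncentrality = d·√(m/2) = 0.5 × √58.25 = 3.816, with 2m − 2 = 231 degrees of freedom.
- One-sided 0.05/30: critical t 2.966, power 80.1%. With 121 per group it is 79.7%, so 122 is exactly the required number.
- Two-sided 0.05/30: critical t 3.181, power 73.6%; 136 per group needed.
- Printed 0.017: 75 per group needed one-sided, 89 two-sided. With 122 per group, power is 95.3% or 92.0%.

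Of these, only one-sided 0.05/30 yields 122 (0.0017, its rounded value, gives the same). Dropout: 122/0.85 = 143.5, so 144, as stated.

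**Step 2: the paired design (signed-rank test).** The paired effect is dz = d/√(2(1 − rho)); noncentrality = dz·√m, with m − 1 = 115.5 degrees of freedom.
- rho = 0: dz = 0.5/√2 = 0.354, noncentrality 3.816
- rho = 0.3: dz = 0.5/√1.4 = 0.423, noncentrality 4.561
- rho = 0.5: dz = 0.5/√1 = 0.5, noncentrality 5.397

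At rho = 0 the noncentrality equals that of the two-group test. The only loss is in degrees of freedom, which raises the one-sided critical t from 2.966 to 2.997.

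| Test | Quantity | rho 0 | rho 0.3 | rho 0.5 |
|---|---|---|---|---|
| One-sided 0.05/30 | Power, 122 pairs | 79% | 94% | 99% |
| | Pairs for 80% | 125 | 89 | 65 |
| Two-sided 0.05/30 | Power, 122 pairs | 72% | 91% | 98% |
| | Pairs for 80% | 139 | 99 | 72 |
| Two-sided 0.017 (as printed) | Power, 122 pairs | 92% | 98% | over 99% |
| | Pairs for 80% | 91 | 65 | 47 |

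For the two-sided 0.05/30 test, power crosses 80% between rho = 0.12 (79.9%) and rho = 0.13 (80.5%).

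**Step 3: detectable effect with 122 pairs at 80% power and alpha 0.05/30.** The detectable dz is 0.357 one-sided and 0.378 two-sided. Multiplying by √(2(1 − rho)) gives d = 0.505, 0.422 and 0.357 one-sided, and 0.534, 0.447 and 0.378 two-sided, at rho = 0, 0.3 and 0.5.

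**Step 4: effect of analysing the sides as independent.** In a simulation of 3,000 runs at rho = 0.3 and two-sided alpha 0.0017, the two-group test had 77% power and the signed-rank test 90%. At nominal alpha 0.017 the two-group test's type I error was about 0.003.

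**The case against.** The strongest reply is that halving does no harm. On the inputs that reproduce 122 it costs about one percentage point at rho = 0 (80.1% to 79.1%), and for positive rho, which the eligibility rule makes likely, it errs on the safe side. That stands. It means the number of patients need not change, but it does not make the stated power a description of this design.

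A reader might infer from the 72% that halving leaves the trial underpowered. The documents do not support this. The 72% needs a two-sided test, which section 2c does not specify, and section 1a frames the aim as superiority over no agent. Two independent groups of 122 already have only 74% power at that alpha, before any halving. At the printed 0.017, 122 pairs have 92% power or more in the two-sided case even at rho = 0. The opposite inference, that enrolment should be cut, is equally unsupported because no rho is given.

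Two further cautions stand. The figures assume normal data, whereas the outcomes include 1-10 ratings and findings such as synechiae and infection, and the questionnaires that would show how each is scored are not in the text. And a non-parametric ANOVA may be a repeated-measures one; section 3d is unclear rather than wrong.

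**Conclusion.** The point holds as a mismatch between the power statement and the design. The stated 80% at d = 0.5 applies to the within-patient comparison only near rho = 0. For assumed rho of 0.3 to 0.5, 122 pairs have 94% to 99% power one-sided at 0.05/30, or 91% to 98% two-sided. A shortfall of any size needs either a two-sided 0.05/30 test with rho below about 0.12, or a negative rho (about 64% at rho = −0.3, one-sided), which the requirement for similar disease on both sides makes unlikely.

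Every rho here is an assumption. The result also rests on d being scaled by the between-patient SD; if d = 0.5 was meant as the paired effect dz, the rho = 0.5 column applies. The misprinted alpha and the unstated sidedness are separate faults in the same paragraph, but power cannot be restated without settling both. This should be corrected; it does not threaten the sample size.

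**What to change.** Keep 122 evaluable and 144 enrolled. In section 2c:
- replace the two-group calculation and the halving with a Wilcoxon signed-rank (matched-pairs) calculation;
- say whether d is scaled by the between-patient SD or by the SD of the side difference;
- state the sidedness;
- print alpha as 0.05/30 = 0.00167;
- report power, or the detectable d from Step 3, at rho = 0, 0.3 and 0.5, labelled as assumptions.

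In section 3d, state that the treated-versus-untreated comparison uses the same paired test.

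The cost is one rewritten paragraph and one added sentence, with no change in enrolment or procedures.
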